367 **Study Procedures.**

Study Procedure	Visit / Follow Up (F/U) Interval										
	Base-line	Medi-cation Review* (Day 1)	PE 1	PE 2	PE 3-4	Interi m Asses s (PE 5)	PE 5-9	Interi m Asses s (PE 10)	PE 10	18 days following medicatio n review	1 Month from completio n of treatment Follow-up
Study Days		1	4	5	6-7	8	8, 11-14	15	15	18	45
Informed Consent	R										
1. Demographics and Military Service Characteristics Form	S,R										
2. Life Events Checklist-5	S,R										
3. Deployment Risk and Resilience Inventory-2	S,R										
4. STRONG STAR Health Questionnaire	S,R										R

5. Prior and Concomitant Medications Interview	S,R									
6. Self-Injurious Thoughts and Behaviors Interview short form	S,R									R
7. Depressive Symptom Index – Suicidality Subscale	S,R		R			R		R		R
8. Clinician-Administered PTSD Scale for the DSM-5(CAPS-5)	S,R									R
9. PTSD Checklist for the DSM-5 (PCL-5)	R		R			R		R		R
10. Patient Health Questionnaire-9	S,R		R			R		R		R
11. Generalized Anxiety Disorder-7	R		R			R		R		R
12. Brief Inventory of Psychosocial Functioning	R									R
13. Veterans RAND 12 Item Short Form Health Survey	R									R
14. Quick Drinking Screen	S,R									R
15. National Institute of Drug Abuse-Quick Screen	S,R									R
16. Insomnia Severity Index	R									R
17. Posttraumatic Cognitions Inventory	R		R			R		R		R
18. Credibility and Expectancy Questionnaire for PE				R						
19. Credibility and Expectancy Questionnaire for CBD				R						
20. AEA, 2-AG (Blood Draw Collection)		R	R			R		R		
21. Cortisol (Saliva Collection)		R	R			R		R		
22. HR Monitoring During Exposure (PE 3, 5, 10)					R		R		R	
23. Adverse Event Monitoring		R**	R	R**	R**	R	R**	R	R**	R**
24. Urine Pregnancy/Drug Screen	S									
25. Liver Function Tests Labs*(LFTs)	S									
26. Massed Prolonged Exposure			R	R	R		R		R	
27. CBD 500mg/daily or placebo daily*		R _{start}	R	R	R		R		R	R _{end}

Table Notes. S=screening purposes; R= Research purposes; *Medication Review Appointment will occur three days prior to beginning Massed Prolonged Exposure. Start and End superscripts represent beginning and end of medication/placebo use. CBD=Cannabidiol; AEA=Anandamide; 2-AG=Arachidonoylglycerol; HR= Heart Rate; *All potential study candidates will be required to complete LFTs or provide a copy of recent LFT labs (completed within 90 days of baseline) and bring their lab results prior to randomization.

*CBD or placebo to be administered daily days 1-18.

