423 cabinets at the STRONG STAR offices. Data will be entered into the STRONG STAR database by a member of the
424 research team.

425 426 7.3.2.1. Instrumentation.

427 See the table in Section 7.3 for a summary of the assessments and timing of administration. A description of each of the
428 assessments can be found at the end of this protocol. Assessments will be administered in person whenever possible.
429 However, to accommodate participant schedules and/or instances in which a participant does not reside in the local area
430 at the time of a follow-up assessment, we may collect full or partial assessments in person or via phone, video
431 conferencing, and/or electronic data capture using a secure link to the encrypted STRONG STAR database. Reasonable
432 efforts will be made to collect all data as described in this protocol, but we expect some participants may not be able to
433 complete part or all of any given follow up assessment.

434 435 7.3.2.2 Data Storage, Access, and Protection.

436 Study files containing hard copies of data collected during study participation will be kept securely at the STRONG STAR
437 offices in San Antonio. Files will be placed into locked cabinets and stored securely in a locked room by a STRONG STAR
438 staff member.

439 Data will be coded using an assigned number. Local study sites will maintain a list of assignment numbers for the purpose
440 of linking subsequent research materials.

441 Data will be entered into the STRONG STAR password protected database housed on a secure UTHSA server by
442 member of the research team. Electronic data will be stored, managed, and analyzed by the STRONG STAR Data and
443 Statistics Services staff of the STRONG STAR consortium. The overall PI and named collaborators will have access to
444 identifiable data through the STRONG STAR website and UTHSA server via direct request to STRONG STAR Data and
445 Statistics Services.

446 All UTHSA STRONG STAR network connectivity is segmented with Access Control Lists and is not accessible to any
447 other UTHSA network segments. The STRONG STAR data server is physically located at the Advanced Data Center
448 (ADC), which has 24x7 onsite security, card key, biometric access controls and video surveillance. UTHSA ADC facility
449 also maintains Gen 2 firewall devices to protect and prohibit any unauthorized access to UTHSA data. All UTHSA network

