 483 monitoring. Secondary endpoints are listed in the table in Section 7.3 and include associated psychopathology, such as
 484 severity scores on measures of depression, general anxiety, disability, and PTSD-related cognitions.

485 **Biospecimens & Heart Rate Monitoring Measures:** We will also assess possible biochemical and physiological
 486 outcomes associated with treatment (Aim 2) and evaluate the relationship between changes in biochemical/physiological
 487 measures with PTSD symptom reductions (Aim 3). To address these aims we will collect blood and saliva samples and
 488 heart monitoring data via a wearable device as described in 7.3.1

489 7.4.3. Data analysis.

490 This pilot study was not powered for formal efficacy or mechanistic hypotheses testing.⁴² Our primary interests are to evaluate
 491 the safety and feasibility of the proposed recruitment, assessment, and treatment protocols; and to detect a signal of possible
 492 PTSD symptom reductions associated with CBD in preparation for a larger trial. To inform future studies, we will calculate
 493 conventional effect sizes with 95% confidence interval limits. Hedges' g will be used to calculate continuous outcome effect
 494 sizes (e.g., CAPS-5, PCL-5). Hedges' g has been recommended over Cohen's d for small samples based on sample size
 495 adjustments yet can be interpreted using the same conventional recommendations as Cohen's d.⁴³

496 Although the statistical power of this study is limited, we will perform statistical analyses appropriate for an adequately
 497 powered study to identify data analysis issues germane to future planning (e.g., data management and scoring, missing
 498 data, data distributions, outliers, trends over time, covariance structures). Statistical analyses will be intent to treat. We will
 499 complete descriptive statistics to describe the study sample and address the feasibility and safety hypotheses. Continuous
 500 outcome measures related to symptom changes and comparison of baseline and posttreatment means will be done with
 501 general or generalized linear mixed effects regression models with repeated measures, with fixed effects of time, group,
 502 and the group by time interaction. Measures with data collected during treatment will also be included in models. Little's⁴⁴
 503 missing completely at random analysis will be completed to confirm likelihood-based model assumptions. Pearson

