663 the IRB Office.** All adverse events, unanticipated problems involving risk to subjects or others, and deviations will be
664 reported to the Institutional Review Board (IRB) in accordance with current IRB policy. UPIRSOs and recurrent non-
665 compliance with study procedures will be reported promptly to the IRB. All adverse events that do not meet the UPIRSO
666 criteria and deviations that are not non-compliance will be summarized at Continuing Review per the IRB of record's policy.
667

10.0. WITHDRAWAL FROM STUDY PARTICIPATION.

668 Participation in the study may be discontinued by the principal investigator if continued participation is considered a
669 danger to a participant's welfare. Reasons for discontinuation include: 1) a serious AE such that continued participation
670 would be a danger to the participant; 2) clinical worsening for any reason that is deemed to necessitate non-study
671 psychological or medical treatment; 3) exacerbation of PTSD, anxiety, or depressive symptoms that the participant cannot
672 tolerate; or 4) drug interactions from concomitant medications that the participant cannot tolerate or would be a danger to
673 the participant; or 5) discontinuation would be in the participant's best interest. Participants deemed candidates for
674 discontinuation will be discussed in conference calls with relevant study team members and will be brought to the
675 attention of the PI and mentor committee for final decision. Participants who are discontinued from the study for any
21-711H, [name], Form BB, 11-15-22, AMD.docx

676 reason will be scheduled for a final evaluation within one week and given appropriate treatment referrals. If participants
 677 are discontinued due to a serious AE, they will continue to be followed clinically by the therapist and/or member of the
 678 research staff until the AE is resolved or becomes stable. The reason the participants are discontinued from the study will
 679 be documented for future study planning.

680 **11.0. TIME REQUIRED TO COMPLETE THE RESEARCH (including data analysis).**

681 The following table provides an overview of activities that the research team plans to accomplish. We anticipate recruiting
 682 and treating two eligible service members per month to meet study goals. We anticipate that the study will be completed
 683 by July 1, 2023.

Study Activities (Months)	Year 1				Year 2			
	0-3	4-6	7-9	10-12	13-15	16-18	19-21	22-24

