752 8. The Clinician Administered PTSD Scale for DSM-5 (CAPS-5).³ The CAPS-5 is a structured interview that assesses the DSM-5 criteria for PTSD. Each item is rated on a severity scale ranging from 0 (Absent) to 4 (Extreme/incapacitating) and combines information about frequency and intensity for each of the 20 symptoms. Additional items that are not included in the total score evaluate overall symptom duration, distress, impairment, dissociative symptoms, and global ratings by the interviewer. Validation studies are nearly complete to establish the psychometric properties of the CAPS-5 and findings will be reported in peer-reviewed publications. This interview is very similar to its predecessor, the CAPS for DSM-IV, which has been considered the gold standard for evaluating PTSD and demonstrated good reliability and validity. In addition to reflecting diagnostic changes for PTSD in DSM-5, the CAPS-5 differs from the CAPS in that frequency and intensity ratings for each symptom are no longer scored separately, so the severity rating for each item determines whether a symptom is present or not. Subscale scores are calculated by summing severity scores for items in the following PTSD symptom clusters: re-experiencing, avoidance, negative alterations in cognitions and mood, and hyperarousal. Scores ≥ 25 indicate a probable diagnosis of PTSD. This measure will be administered at the baseline assessment and the one-month follow-up assessment.

753

754

755

756

757

758

759

760

761

762

763

764

765

766 9. PTSD CheckList-5 (PCL-5).⁴ The PCL-5 is a 20-item self-report measure update of the PCL designed to assess PTSD symptoms as defined by the DSM-5. The PCL-5 is currently available and has been shown to have good psychometric properties. The PCL-5 evaluates how much participants have been bothered by PTSD symptoms in the past week (for all assessments during treatment) or the past two weeks (all other assessment time points) as a result of a specific life event. Each item of the PCL-5 is scored on a five-point scale ranging from 0 "not at all" to 4 "extremely". This measure will be administered at the baseline assessment, the interim assessments, and the one-month follow-up assessment.

767

768

769

770

771

772

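### The plan does not say that participants discontinued from the study keep the Day 45 follow-up, the only scheduled post-baseline CAPS-5, although the analysis is called intent to treat

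*Combined protocol and SAP*

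**What the plan says.** **Withdrawal rule (Section 10.0).** The rule opens "Participants who are discontinued from the study for any" and continues "reason will be scheduled for a final evaluation within one week and given appropriate treatment referrals". The evaluation's content is not given. The listed grounds are a serious adverse event, clinical worsening that needs treatment outside the study, symptom exacerbation or drug interactions that the participant cannot tolerate, and the participant's best interest.

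**CAPS-5 (Section 14.0, item 8).** Scores at or above 25 "indicate a probable diagnosis of PTSD. This measure will be administered at the baseline assessment and the one-month follow-up assessment". The Section 7.3 table agrees and places the follow-up at Study Day 45.

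**PCL-5 (Section 14.0, item 9).** It is "administered at the baseline assessment, the interim assessments, and the one-month follow-up assessment", so it has three further scheduled scores, at PE sessions 1, 5 and 10.

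**Outcomes and analysis.** Section 7.4.2 makes the CAPS-5 total, the PCL-5 total and adverse events the primary outcomes. Section 7.4.3 states "Statistical analyses will be intent to treat" and specifies mixed models with time, group and their interaction, plus Little's test. Against attrition it offers frequent contact and asks those who stop treatment for their reasons.

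**Remote assessment (Section 7.3.2.1).** To fit participants' schedules or location, "we may collect full or partial assessments in person or via phone, video" or electronic capture.

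**The concern.** An intent-to-treat analysis needs more than a label. It needs outcome data, as far as they can be had, from everyone randomised at the time being compared. The withdrawal rule provides a visit at a time tied to discontinuation, and no text secures the scheduled one. PCL-5 leaves earlier scores to work with, but CAPS-5 has nothing between baseline and Day 45.

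The absences would probably not be random. Worsening and intolerable exacerbation of PTSD symptoms are close to the outcome itself, and adverse events or drug interactions may occur more often in one arm. If participants who would have scored worse are lost unequally, the arm that loses more of them looks better than it should.

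The purpose of this pilot is to give effect sizes with 95% confidence intervals for planning a larger trial, so such a bias would be carried forward into that design.

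**Working it through.** **1. The plan's own figures (Section 7.4.1).** 24 evaluable + 4 dropouts or withdrawals = 28 randomised. The stated 17% is 4/24 = 16.7%; as a share of those randomised it is 4/28 = 14.3%. With 30% screen failure, 28/(1 − 0.30) = 40 to consent. The figures reproduce. There is no power calculation to check.

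**2. Can the one-week evaluation stand in for Day 45?** The medication runs from Day 1 to Day 18.

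| Discontinued on | Latest evaluation | Days before Day 45 |
|---|---|---|
| Day 1 | 1 + 7 = 8 | 45 − 8 = 37 |
| Day 8 | 8 + 7 = 15 | 45 − 15 = 30 |
| Day 18 | 18 + 7 = 25 | 45 − 25 = 20 |

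The evaluation could reach Day 45 only if discontinuation came on or after Day 38 (45 − 7). For anyone discontinued during the medication period, even an evaluation that included CAPS-5 would fall at least 20 days early, and the plan does not say how such a score would enter the model.

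**3. What the mixed model can recover for CAPS-5.** With two time points and follow-up missing for some, the likelihood estimate of an arm's follow-up mean is the completers' mean, adjusted by the regression on baseline for any difference between the baseline mean of all participants and that of completers. Baseline-only participants therefore contribute a little. The model corrects only the part of their shortfall that baseline CAPS-5 predicts. Worsening that arises during treatment is not in the baseline score.

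**4. Possible size of the bias.** Assumptions, none from the documents except the 4 and the 28: equal allocation (14 per arm), all 4 losses missing at Day 45, and missing scores worse than completers' by D = 0.5 to 1 SD, read as the gap that baseline does not explain. Then

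bias = D × (difference between arms in the fraction missing).

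| Split of 4 losses | Difference in fraction | D = 0.5 | D = 1 |
|---|---|---|---|
| 2:2 | 2/14 − 2/14 = 0 | 0 | 0 |
| 3:1 | 3/14 − 1/14 = 0.143 | 0.07 SD | 0.14 SD |
| 4:0 | 4/14 − 0 = 0.286 | 0.14 SD | 0.29 SD |

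The bias favours the arm with more losses.

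**5. Precision, separately.** The standard error with 12 v 12 relative to 14 v 14 is √(28/24) = 1.08, about 8% larger. That figure belongs to the 2:2 split, where the illustrated bias is zero. With 10 v 14 the ratio is √[(1/10 + 1/14)/(1/14 + 1/14)] = √(0.1714/0.1429) = 1.10. The approximate 95% half-width for Hedges' g at g = 0 is 0.72 with 14 v 14, 0.77 with 12 v 12 and 0.78 with 10 v 14.

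**The case against.** A reader might infer that the one-week evaluation replaces the Day 45 visit. The text does not say so. The inference rests on the word final, on the heading about withdrawal, on a follow-up timed from completion of treatment, and on the sample-size table, which sets completed or evaluable participants apart from those who leave. The evaluation could include CAPS-5 and PCL-5, and Day 45 is not cancelled. This part of the objection stands: the defect is a rule left unstated.

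Other parts also stand:

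- **Scope.** Section 10.0 concerns discontinuation from the study. Section 7.4.3 mentions stopping treatment separately, and nothing says that those participants lose Day 45. Section 7.3.2.1 also promises reasonable efforts to collect all data.
- **PCL-5.** A reader might infer that both symptom outcomes are lost. They are not, because PCL-5 scores collected during treatment enter the model.
- **Completer analysis.** It is tempting to say that CAPS-5 becomes a pure completer analysis. Baseline-only participants add little, but not nothing.
- **Number lost.** The 4 covers dropout of every kind, and some of those people might miss Day 45 under any rule.
- **Scale.** Even 0.29 SD lies well inside the planned uncertainty, and the pilot is declared not powered for efficacy testing.

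What does not stand is the conclusion that no change is needed. A promise to collect data as described does not help where no collection is described. Little's test cannot show that absence is unrelated to unseen scores, and it has little power with about four losses. Wide intervals do not excuse a bias that can be reduced by asking participants back.

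**Conclusion.** The point holds as a gap in the plan. Participants discontinued from the study have an undefined evaluation within a week and no stated Day 45 assessment, so their CAPS-5 at the only scheduled post-baseline point is missing or, at best, replaced by an off-schedule score with no stated use. That sits badly with an intent-to-treat claim, and several grounds for discontinuation make outcome-related absence plausible, though not demonstrated.

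The illustrated bias in the CAPS-5 contrast runs from 0 to 0.29 SD. The upper end needs all four planned losses in one arm and a full 1 SD difference. It is an upper planning figure for this route and not a forecast.

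The sponsor should make the change. Confidence is moderate: the silence and the CAPS-5 schedule are clear from the text, but the sponsor's intention for Day 45 is not.

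**What to change.** 1. Separate stopping study drug or mPE from ending outcome assessment. State that, unless consent for follow-up is withdrawn, every randomised participant is invited to the Day 45 CAPS-5 and PCL-5 and is analysed in the arm to which they were randomised. Remote assessment is already permitted by Section 7.3.2.1, and Section 7.5 allows interviews by video.
2. Keep the one-week evaluation as an additional visit. List its instruments, and say whether and how any CAPS-5 or PCL-5 score from it enters the mixed model.
3. For participants who never reach the end of treatment, tie the follow-up to Study Day 45 so that the visit has a defined date.

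The discontinuation criteria stay as they are. The cost is a short amendment and, on the plan's own dropout figure, at most about four more follow-up assessments of a type already in the schedule. The documents do not show whether these are budgeted.
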